14.6.1 Major cardiovascular events

Major adverse cardiovascular events (MACE) will be tabulated separately and will be identified using the following UCB-defined search criteria:

- All serious TEAEs which code to a PT included in the search = Broad scope of the following standardized MedDRA queries (SMQ):
 - Haemorrhagic central nervous system vascular disorders
 - Ischaemic central nervous system vascular disorders
- All serious TEAEs which code to a PT included in the HLT = ‘Ischaemic coronary artery disorders’ except events coding to PT = ‘Chest pain’ or PT = ‘Chest discomfort’
- All serious TEAEs which code to a PT included in any of the following HLTs: “Heart Failures NEC”, “Left Ventricular Failures”, or “Right Ventricular Failures” and which also code to the SOC of “Cardiac Disorders” as the Primary SOC

14.6.2 Serious infections, including opportunistic infections and tuberculosis

14.6.2.1 Serious infections

Serious infections are based on MedDRA classification using the SOC = ‘Infections and Infestations’. Such events will be included in the tabulations of SAEs and no separate summary tabulations will be presented.

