#### **12.1.3 Adverse events for special monitoring**

UCB has identified AEs for special monitoring (AESM). An AESM is an AE or safety topic for which special monitoring, additional data collection activities, and/or enhanced signal detection activities (within UCB), are considered appropriate. Identified AESM can be of particular interest based on findings from the IMP clinical program to date, potential risks generally associated with biologic immunomodulators, or comorbidities and risk factors prevalent in the study population.

Adverse events for special monitoring for this study include: serious infections (including opportunistic infections and TB, see [Section 12.6.1](#)), cytopenias, hypersensitivities, suicide ideation or behavior (assessed using the C-SSRS), depression and anxiety (assessed using the

HADS, see [Section 9.4](#) ), major cardiovascular events and liver function test changes/enzyme elevations (ALT, AST, and bilirubin; see [Section 12.5.1](#)), and malignancies and inflammatory bowel diseases.

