11.1.3 Subject time at risk

The subject time at risk represents the time a subject was at risk for having an AE and will be used to calculate the exposure adjusted incidence rate (EAIR) and exposure adjusted event rate (EAER) as described in [Section 11.2](#).

The subject time at risk (days) will be calculated as follows:

$$\text{Time at risk} = (\text{Date of Last Dose} - \text{Date of First Dose}) + 140 \quad [11]$$

In cases where the last clinical contact or last visit occurs prior to completion of the SFU period, the subject time at risk is calculated as follows:

$$\text{Time at risk} = (\text{Date of Last Contact} - \text{Date of First Dose}) + 1 \quad [12]$$

This will apply for the following:

- For subjects entering the extension study the date of last contact (in PS0016) refers to the date of the visit at which they enter the extension study (ie, Week 20, 24, 28 or 36)
- For subjects that discontinue prematurely (ie, and no SFU data are available), the date of final contact refers to the date of the latest contact with the subject during the study after

which no further information or data are available. This will be reported on the study termination page of the CRF.

- For subjects that have died during the study the date of last contact refers to the date of death
- Subject-years at risk is defined as the subject time at risk divided by 365.25. The days at risk and subject-years at risk will be listed together with the drug administration information (Section 11.1.1).

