11.2 Adverse events

11.2.1 Definitions and classification of adverse events

All AEs will be recorded in the CRF from informed consent until study completion or termination.

Adverse events with start date prior to the first administration of IMP are defined as pre-treatment AEs. A TEAE is defined as any AE with a start date/time at the time of or after the first administration of IMP up until the last received dose of IMP + 140 days (which covers the 20 week SFU Period). Adverse events occurring after this date will not be classified as TEAEs and will therefore be excluded from the summary tables.

Where dates are missing or partially missing, AEs will be assumed to be treatment-emergent, unless there is clear evidence to suggest that the AE started prior to dosing. Handling of missing dates/times for classification of AEs as TEAEs is described in Section 4.2.4.

In order to allow for a comparative period across all subjects, prior to the point at which subjects are eligible to enter the extension study, TEAEs will be classified as follows:

- **Treatment Period TEAEs:** all TEAEs with onset at the time of or after the first administration of IMP up until the Week 20 visit. Any TEAEs that occur on the date of the Week 20 visit will be included (ie, the cut off will be assumed to be at 23:59 hours on the date of Week 20). Such TEAEs will be designated as 'Treatment Period' TEAEs in the tabulations. Any subjects that withdraw prior to Week 20 will have Treatment Period TEAEs cut off at 140 days relative to the first dose (ie, equivalent to 20 weeks).
- **Post-Treatment Period TEAEs:** all TEAEs with onset after the Week 20 visit up until the last dose of IMP + 140 days will be designated as 'Post-Treatment' TEAEs in the tabulations. Thus, any tabulation including Post-Treatment TEAEs will include only those TEAEs for subjects not entering the extension study at all or those TEAEs for subjects who enter the extension study at a later visit. For subjects that withdraw prior to Week 20, Post-Treatment Period TEAEs are classified as those starting after 140 days relative to the first dose (ie, equivalent to 20 weeks).

For the EAIR and EAER tabulations the above classifications will not be applicable, as these summaries are, by definition, adjusted for the individual exposure at risk for each subject.

All AEs will be coded and categorized by intensity (mild/moderate/severe) and relationship to IMP (related/not related).

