11.2.3 Presentation of adverse events

An overview of the number and percentage of subjects who experience TEAEs will be presented by treatment group (including All Subjects), based on the SS. This tabulation will include the number and percentage of subjects with any TEAEs, serious TEAEs, related TEAEs, discontinuation due to TEAEs, severe TEAEs, AEs leading to death and TEAEs leading to death; event counts will also be included. The tabulation will be repeated for Treatment Period TEAEs and Overall TEAEs.

In addition, the following summaries will be presented by treatment group (including All Subjects), SOC, high level term (HLT) and PT, based on the SS:

- Incidence of TEAEs during Treatment Period
- Incidence of TEAEs Overall
- Incidence of serious TEAEs during Treatment Period
- Incidence of serious TEAEs Overall

-
- Incidence of non-serious TEAEs during Treatment Period
 - Incidence of non-serious TEAEs Overall
 - Incidence of TEAEs during Treatment Period by relationship
 - Incidence of TEAEs Overall by relationship
 - Incidence of TEAEs during Treatment Period by maximum relationship
 - Incidence of TEAEs Overall by maximum relationship
 - Incidence of TEAEs during Treatment Period by maximum intensity
 - Incidence of TEAEs Overall by maximum intensity
 - Incidence of fatal TEAEs during Treatment Period by relationship
 - Incidence of fatal TEAEs Overall by relationship
 - Incidence of non-serious TEAEs during Treatment Period by relationship
 - Incidence of non-serious TEAEs Overall by relationship
 - Incidence of serious TEAEs during Treatment Period by relationship
 - Incidence of serious TEAEs Overall by relationship
 - Incidence of non-serious TEAEs during Treatment Period above threshold of 5% of subjects
 - Incidence of non-serious TEAEs Overall above threshold of 5% of subjects
 - Incidence of non-serious TEAEs during Treatment Period above threshold of 5% of subjects by relationship
 - Incidence of non-serious TEAEs Overall above threshold of 5% of subjects by relationship
 - Incidence of TEAEs during Treatment Period by SOC and PT (including the number and percentage of subjects and individual subject numbers/reported terms for each PT stratified by intensity, relationship and seriousness)
 - Incidence of TEAEs (including all TEAEs during Treatment and Post-Treatment Periods) by SOC, HLT and PT and including the EAIR and EAER calculated as described in [Section 11.2.2](#)

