 - Incidence of TEAEs (including all TEAEs during Treatment and Post-Treatment Periods) by SOC, HLT and PT and including the EAIR and EAER, stratified by overall ADA status (positive/negative)

In addition, separate AE summaries by treatment group, SOC, HLT and PT (including all TEAEs during Treatment and Post-Treatment Periods combined) will be included for the following AEs of special monitoring (AESM):

- Major cardiovascular events
- Serious infections, including opportunistic infections and tuberculosis (TB)
- Malignancies including lymphoma

- Cytopenias
- Neuropsychiatric events (in particular, depression and suicide)
- Inflammatory bowel disease
- Anaphylactic reaction (hypersensitivity and anaphylactic reactions)
- Hepatic events and drug-induced liver injury

All summary tables (including those for AESM) will contain the number and percentage of subjects and the number of events where applicable. A subject who has multiple events in the same SOC, HLT and PT will be counted only once in the subject counts but all events will be included. In addition, for all tabulations of AESM, the EAER and EAIR will be reported.

The criteria for identifying AESM and additional criteria for reporting AESM are provided in [Section 14.6](#).

In summaries including relationship to IMP, the following relationship categories will be included:

- Related
- Not related

Subjects who experience the same event multiple times will be included in the most related category for tabulations by maximum relationship. Events with missing relationship will be considered as 'Related' for summary purposes but shown as missing in the data listings.

In summaries including intensity, the following categories will be summarized:

- Mild
- Moderate
- Severe

Subjects who experience the same event multiple times will be included in the most severe category for tabulations by maximum intensity. Events with missing intensity will be considered as severe for summary purposes. All data will be presented as recorded in the database for the listings.

Adverse event summaries will be ordered by alphabetical SOC, alphabetical HLT within SOC and decreasing frequency of PT in the 'BKZ 320mg' (Treatment arm B) column for tables including event counts. For tables including only number and percentage of subjects, summaries will be ordered by alphabetical SOC, alphabetical HLT within SOC and decreasing incidence of PT within HLT and SOC in the 'BKZ 320mg' (Treatment arm B) column.

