14.6 Adverse events of special monitoring

The following AESM are defined for bimekizumab and will be summarized separately as described in [Section 11.2](#):

- Major cardiovascular events
- Serious infections, including opportunistic infections and TB

- Malignancies including lymphoma
- Cytopenias
- Neuropsychiatric events (in particular, depression and suicide)
- Inflammatory bowel disease
- Anaphylactic reaction (hypersensitivity and anaphylactic reactions)
- Hepatic events and drug-induced liver injury

All AESM tabulations will be presented by treatment group, SOC, HLT and PT, based on the SS, and will include the EAIR and EAER.

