14.6.2.3 Opportunistic infections

Opportunistic infections (including TB) will be summarized in a separate table including all TEAEs identified using search criteria defined by UCB.

Opportunistic infections are identified in 2 steps:

- Step 1: Refer to column B of the spreadsheet which identifies the PTs to be classified as opportunistic infections using either a single ‘x’ or a double ‘xx’.

- All TEAEs which code to a PT flagged with a single ‘x’ need to also be serious in order to be considered an opportunistic infection.
- All TEAEs which code to a PT flagged with a double ‘xx’ are considered to be an opportunistic infection, regardless of seriousness.

All serious TEAEs in the study database which code to a PT flagged with a single ‘x’ and all TEAEs in the study database which code to a PT flagged with a double ‘xx’ will be summarized as an opportunistic infection in the stand-alone table.

- Step 2: Refer to column C of the spreadsheet which identifies the PTs that need to be evaluated on a case-by-case basis by the study physician in order to determine whether it is a true opportunistic infection or not. The process for physician review is as follows:
 - Study programming team creates a spreadsheet which lists all of the subjects with a TEAE present in the database which codes to a PT identified as needing case-by-case review. Information from the AE dataset to be included in the spreadsheet: Subject ID, AE verbatim term, SOC, HLT, Lower Level Term (LLT), PT, AE start date, AE end date, seriousness, severity, relationship to study medication, action taken. Additionally, a column will be included where the study physician can document their decision on the case.
 - Study physician reviews the cases in the spreadsheet and indicates in the additional column which AEs are confirmed to be opportunistic infections via a single ‘x’.
 - Study programming team incorporates these decisions into the analysis data adverse events (ADAE) dataset by merging the study physician decisions for individual subjects / PTs and flagging the confirmed opportunistic infections as such in the dataset.

All subjects with an AE reported that has been confirmed by the study physician to be an opportunistic infection (based on case-by-case review) will be summarized as such in the stand-alone table, together with all of the events identified in Step 1 of this process.

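### Serious infections are a listed event for special monitoring, but the SAP plans neither a separate table nor an exposure-adjusted rate for them as a whole

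*SAP*

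**What the plan says.** Protocol 12.1.3 puts this category first in its list: "Adverse events for special monitoring for this study include: serious infections (including opportunistic infections and TB", followed by the other topics.

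The SAP carries the category over as one of eight AESM, in 11.2.3 and again in 14.6. Section 11.2.3 plans separate summaries for the listed AESM and adds that "for all tabulations of AESM, the EAER and EAIR will be reported". Section 14.6 says that the listed AESM are summarized separately and sets the content: "All AESM tabulations will be presented by treatment group, SOC, HLT and PT, based on the SS, and will include the EAIR and EAER".

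SAP 14.6.2 divides the infection category into three:

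- 14.6.2.1, serious infections, identified through the MedDRA infections SOC: "Such events will be included in the tabulations of SAEs and no separate summary tabulations will be presented".
- 14.6.2.2, fungal infections: a separate summary, although the AESM list does not name them.
- 14.6.2.3: "Opportunistic infections (including TB) will be summarized in a separate table".

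**The concern.** Two general sections call for a separate table with rates for every listed AESM, and one subsection withdraws it for serious infections. No stated exception connects them. Limiting the category to serious events does not explain the difference, because major cardiovascular events (14.6.1) are also restricted to serious TEAEs and are tabulated separately.

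What is at stake is the exposure adjustment. Subjects who relapse can leave for the extension study from Week 20, so follow-up lengths differ. Arm A receives placebo at Week 16 and arm B receives active drug, so early exit could plausibly differ between arms, although the documents give no expected rates. Over full follow-up, a plain percentage of subjects with a serious infection does not account for this. EAIR and EAER do, and the SAP specifies them for AESM tables.

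**Working it through.** The plan states no figure on this point, so there is none to reproduce. The check compares the passages and the planned outputs, then sizes the missing rate with the SAP's own formulas.

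**Coverage of the AESM list.** Seven of the eight listed AESM have a tabulation in their own subsection (14.6.1 and 14.6.3 to 14.6.8). The eighth has one for its opportunistic/TB part only.

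**What the planned outputs show for serious infections as a whole.**

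| Planned output (SAP section) | Serious infections identifiable? | Exposure-adjusted? |
|---|---|---|
| Serious-TEAE tables, Treatment Period and Overall (11.2.3) | Yes, in the infections SOC rows | No, incidence only |
| All-TEAE table with EAIR and EAER (11.2.3) | No, serious and non-serious events together | Yes |
| Opportunistic infections incl. TB (14.6.2.3) | That part only | Yes, under 14.6 |
| Fungal infections (14.6.2.2) | Fungal only, any seriousness | Yes, if treated as an AESM table |
| SAE listings (11.2.3) and subject-years listing (11.1.3) | Yes, by subject | Only if derived by hand |

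**Time at risk (SAP 11.1.3).** Inputs are nominal visit days, with all three doses given.

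- Formula [11], full follow-up: (112 − 0) + 140 = 252 days.
- Formula [12] applies "In cases where the last clinical contact or last visit occurs prior to completion of the SFU period", and 11.1.3 applies it to subjects entering the extension: Week 20, 140 + 1 = 141 days; Week 24, 168 + 1 = 169 days; Week 28, 196 + 1 = 197 days.
- A Week 20 entrant therefore contributes 141/252 = 56% of full time at risk.

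**Size of the rate.** EAIR = 100 × n / subject-years (formula [13]). For n = 1 the exact Poisson limits (formula [14]) are 0.0253 and 5.572 events, divided by subject-years and scaled to 100. Planned arm sizes are 30 and 15. The share entering the extension at Week 20 is my assumption, because the documents give none.

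| Arm, share entering at Week 20 | Mean days | Subject-years | EAIR for 1 event (95% CI) |
|---|---|---|---|
| A, 0% | 252 | 30 × 252 / 365.25 = 20.70 | 4.8 (0.12 to 26.9) |
| A, 25% | 224.25 | 18.42 | 5.4 (0.14 to 30.2) |
| A, 50% | 196.5 | 16.14 | 6.2 (0.16 to 34.5) |
| B, 0% | 252 | 15 × 252 / 365.25 = 10.35 | 9.7 (0.24 to 53.8) |

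Relative to no early entry, the arm A rate rises by 252/224.25 = 1.12 and 252/196.5 = 1.28. If entry is at Week 28 instead, the ratios are 252/238.25 = 1.06 and 252/224.5 = 1.12. For a between-arm contrast, suppose 50% of arm A and nobody in arm B entered at Week 20. Equal crude percentages would then hide a rate ratio of about 1.28.

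These figures ignore the rule in 11.2.2 that the affected subject's time stops at onset. If onset were near day 0, the arm A rate with no early entry would be 100 / (29 × 252 / 365.25) = 5.0 instead of 4.8.

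**The case against.** The strongest reply is that 14.6.2.1 is a deliberate exception. Section 11.2.3 refers to 14.6 for further reporting rules, 14.6.2.1 is the only text specific to serious infections as such, and it is unambiguous. On that view the EAIR and EAER sentences govern only those AESM tables that are produced. This is a fair reading, and a programmer could follow it. It does not remove the mismatch: 11.2.3 and 14.6 would still promise a separate summary for a listed AESM without saying that one is exempt.

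The second reply is that coverage is already wide, and this stands. Serious infections are counted by SOC, HLT and PT in two sets of tables. One of these, "Incidence of serious TEAEs during Treatment Period", uses the Week 20 cut-off adopted "In order to allow for a comparative period across all subjects". The opportunistic/TB part of the same AESM has its own table. A rate could also be worked out from the listings. A reader might infer that serious infections would go unreported, or that the arms could not be compared. The documents do not support either inference.

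The third reply is that in an exploratory study of about 45 subjects the interval swamps any exposure effect. That is correct as to size: an interval of 0.12 to 26.9 is far wider than a 1.28-fold shift.

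**Conclusion.** The point holds in a narrow form. The SAP's general AESM rule and 14.6.2.1 do not agree, and no planned output gives an exposure-adjusted rate for serious infections as a whole. Reading 14.6.2.1 as an intended exception settles what to program, but it leaves 11.2.3 and 14.6 wrong as written. The mismatch lies within the SAP: the protocol names the category but does not itself prescribe the table.

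The effect is small and limited to safety reporting. The sizes above rest on nominal visit days, planned arm sizes, one assumed event and assumed extension-entry shares.

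Two nearby items could be taken for errors, and the documents do not establish either. First, item 7 of Category D in 14.6.7.1, Diastolic hypertension, runs against the other blood-pressure terms in that list, which are decreases or hypotension. No passage limits the category to falls in pressure, and the MedDRA query itself is not reproduced, so this is only a query. Second, Table 14-5 has no row applying the ALP condition of the potential Hy's Law definition in protocol 12.1.2. The existing bilirubin and transaminase row is broader on ALP and is not labelled as Hy's Law, and 14.6.8 provides for adjudication. This is a labelling note, not a contradiction.

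**What to change.** Reconcile 14.6.2.1 with 11.2.3 and 14.6. The preferred change is to replace the last sentence of 14.6.2.1 with a table of serious TEAEs in the infections SOC, by treatment group, SOC, HLT and PT, based on the Safety Set and both periods combined, with EAIR and EAER. This follows the SAP's own general rule. If the exception is intended, state it in 11.2.3 and 14.6 and give the reason.

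The cost is one small table from data already collected, or a sentence in each of two sections.

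As a side check, compare Category D item 7 with the version of the MedDRA query in use. Optionally, label the Table 14-5 row used for Hy's Law cases and say whether the ALP condition is applied in the table or at adjudication.

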14.6.2.2 Fungal infections

Fungal infections will be summarized separately based on all TEAEs coding to the high level group term (HLGT) = ‘Fungal infectious disorders’.

14.6.2.3 Opportunistic infections

Opportunistic infections (including TB) will be summarized in a separate table including all TEAEs identified using search criteria defined by UCB.

Opportunistic infections are identified in 2 steps:

- Step 1: Refer to column B of the spreadsheet which identifies the PTs to be classified as opportunistic infections using either a single ‘x’ or a double ‘xx’.

- All TEAEs which code to a PT flagged with a single ‘x’ need to also be serious in order to be considered an opportunistic infection.
- All TEAEs which code to a PT flagged with a double ‘xx’ are considered to be an opportunistic infection, regardless of seriousness.

All serious TEAEs in the study database which code to a PT flagged with a single ‘x’ and all TEAEs in the study database which code to a PT flagged with a double ‘xx’ will be summarized as an opportunistic infection in the stand-alone table.

- Step 2: Refer to column C of the spreadsheet which identifies the PTs that need to be evaluated on a case-by-case basis by the study physician in order to determine whether it is a true opportunistic infection or not. The process for physician review is as follows:
 - Study programming team creates a spreadsheet which lists all of the subjects with a TEAE present in the database which codes to a PT identified as needing case-by-case review. Information from the AE dataset to be included in the spreadsheet: Subject ID, AE verbatim term, SOC, HLT, Lower Level Term (LLT), PT, AE start date, AE end date, seriousness, severity, relationship to study medication, action taken. Additionally, a column will be included where the study physician can document their decision on the case.
 - Study physician reviews the cases in the spreadsheet and indicates in the additional column which AEs are confirmed to be opportunistic infections via a single ‘x’.
 - Study programming team incorporates these decisions into the analysis data adverse events (ADAE) dataset by merging the study physician decisions for individual subjects / PTs and flagging the confirmed opportunistic infections as such in the dataset.

All subjects with an AE reported that has been confirmed by the study physician to be an opportunistic infection (based on case-by-case review) will be summarized as such in the stand-alone table, together with all of the events identified in Step 1 of this process.

The timing and frequency of Step 2 should be outlined and agreed to by the study team at the beginning of the study.

Following the initial physician review of case-by-case events, subsequent reviews will be based on the cumulative set of case-by-case events present in the database at each timepoint of spreadsheet creation. Physician decisions from previous runs should be retained in each subsequent run. The final run of the spreadsheet, with all study physician decisions on the full set of case-by-case events, will be archived at the conclusion of the study.

